13 PLANNED STATISTICAL METHODS

A detailed description of data analysis and statistical methods to be used will be outlined separately in the statistical analysis plan.

13.1 General Considerations

Part 1 (Phase 1)

Analyses for the primary safety endpoint will be descriptive. AEs will be classified using MedDRA version 20.0 or higher. The severity of the toxicities will be graded according to the NCI CTCAE version 5.0.

Part 2 (Phase 2a)

In the randomized, Phase 2 portion of the study, the primary efficacy endpoint is time to recovery, defined as the first day during the 28 days after randomization on which a subject meets the criteria for category 0, 1, 2, 3, or 4 on the WHO severity scale for COVID-19 pulmonary syndrome. The intent-to-treat (ITT) analysis will be carried out for the primary efficacy endpoint. Subjects will be analyzed according to the assigned treatment group, regardless of whether the subjects receive any study treatment or receive a different study treatment from that to which they were randomized. The primary analysis will be a stratified log-rank test of time to recovery with cePolyTregs compared with placebo/SOC, with stratification by WHO severity scale for COVID-19 pulmonary syndrome at enrollment. The test will be performed with a two-sided type I error rate of 10%. Data for subjects who fail to recover or die will be censored at Day 29.

Analysis of the primary safety endpoint will be descriptive according to the intervention received and no formal comparisons between the 2 study arms will be performed. The safety analysis set will consist of all subjects who received at least 1 dose of study drug. AEs will be summarized by dose cohort using numbers and proportions.

The assessment of PD and biomarker data are described in [Appendix C Mechanistic Assessments](#).

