8.3 Rationale for Study Design

Part 1 of this study will be an open-label, dose escalation trial. On-treatment safety and changes in PD measures will be monitored to determine the safety of cePolyTregs and identify the RP2D for further study in Part 2. Safety and tolerability of cePolyTregs will be evaluated by continuous assessment of AEs, vital signs, ECGs, clinical laboratory parameters, and chest imaging. The PD and biomarker profile associated with cePolyTregs will be evaluated through serial blood sampling. Dose escalation will occur by cohort following review of data by the DSMB to allow emerging safety, PD, and other data to inform dose escalation decisions based on pre-defined DLT criteria and stopping rules.

Part 2 of this study has a randomized, double-blinded, placebo-controlled design to minimize bias in allocation of subjects to treatment assignment and evaluation of safety and clinical activity.

These design features are intended to minimize risk to subjects and to allow exploration of a safe range of doses over relatively short treatment duration as well as to explore doses associated with PD and clinical activity.

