8.6 Endpoints

8.6.1 Primary Endpoints

Part 1 (Phase 1):

Safety and tolerability of cePolyTregs as assessed by DLTs, defined as any related treatment-emergent adverse event (TEAE) with an NCI CTCAE 5.0 grade ≥ 3 which also represents a shift from baseline clinical status of ≥ 1 NCI CTCAE grade.

Part 2 (Phase 2a):

Efficacy of cePolyTregs compared with placebo/SOC, as assessed by time to recovery, defined as the first day during the 28 days after randomization on which a subject meets the criteria for category 0, 1, 2, 3, or 4 on the WHO severity scale for COVID-19 pulmonary syndrome.

Safety of cePolyTregs as assessed by the occurrence of related TEAEs with an NCI CTCAE 5.0 grade ≥ 3 .

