13.2 Determination of Sample Size

In Part 2 of the study, a total of 100 subjects will be randomized 1:1 to receive cePolyTregs or placebo/SOC administered as a single IV dose. Randomization will be stratified by study site and baseline WHO severity scale for COVID-19 pulmonary syndrome. Beigel (2020) reported that the rate of achieving a clinical severity score of 4 or better was 26.6% (67 out of 252 patients) within 14 days in the placebo arm among those with a symptom score ≥ 6 . Assuming that the distribution of time to recovery follows an exponential distribution, a 26.6% recovery rate within 14 days is equivalent to a median time to recovery of 31.4 days and a 46.1% recovery rate within 28 days. We expect cePolyTregs will halve the median time to recovery to 16 days, which is

equivalent to recovery rates of 45.5% and 70.2% within 14 and 28 days, respectively, under the exponential assumption. A sample size of 100 subjects (50 per group) will have 80% power to detect a reduction of 15.4 days in median time to recovery (or, equivalently, an improvement in recovery rate from 46.1% to 70.2% within 28 days) using the log-rank test at a two-sided type I error rate of 10%, based on Monte-Carlo simulations with 10,000 replicates.

The planned sample size will also provide a reasonably accurate estimate of the true SAE rate. The remdesivir study ([Beigel 2020](#)) reported that 30% of patients in the placebo group encountered SAEs. If 15 (30%) out of the 50 subjects in a study arm of the present study are observed to have an SAE, it will be possible to conclude that the true SAE rate is lower than 45%, at a 5% error rate, because the 95% confidence interval (0.179, 0.446) will exclude 45%.

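### Part 2 plans no between-arm estimate or interval for its primary safety endpoint, and the only stated safety precision is a one-arm SAE figure that does not use the placebo arm

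*Combined protocol and SAP*

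**What the plan says.** Section 8.5.1 makes safety and tolerability a primary objective of both parts. For Part 2, section 8.6.1 defines a primary safety endpoint: "Safety of cePolyTregs as assessed by the occurrence of related TEAEs with an NCI CTCAE 5.0 grade" (the threshold is grade 3 or higher). Section 8.3 explains that Part 2 has a "placebo-controlled design to minimize bias in allocation of subjects to treatment assignment and evaluation of safety and clinical activity".

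Section 13.1, repeated in the synopsis, then says: "Analysis of the primary safety endpoint will be descriptive according to the intervention received". About the randomized groups it adds that "no formal comparisons between the 2 study arms will be performed". Section 13.6 lists incidence tables by system organ class, preferred term, worst grade and relationship. It names no difference, ratio or interval. By contrast, section 13.8 plans chi-squared or Fisher tests between arms for categorical efficacy variables.

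Section 13.2 holds the one inferential statement on adverse-event rates. It cites an outside trial that "reported that 30% of patients in the placebo group encountered SAEs". It then supposes 15 subjects with an SAE among the 50 in either arm, and from this claims that "it will be possible to conclude that the true SAE rate is lower than 45%, at a 5% error rate". The interval offered in support runs from 0.179 to 0.446.

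The analysis set is described in two ways. Sections 13.1 and 13.3.1 include everyone who received study drug. The Safety Analyses paragraph of the synopsis refers only to recipients of cePolyTregs.

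**The concern.** In ventilated patients with ARDS the background rate of serious events is high, so the rate in one arm mixes what the cells do with what the illness does. The concurrent placebo arm is the means of separating them, and the plan makes no inferential use of it for adverse events.

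Two features of the protocol make the control more important:

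- Section 12.5 counts an event as related if there is at least some possibility of a link, and section 10.7 keeps investigators blinded. Placebo recipients can therefore also accrue related events, and the count on cells alone does not isolate product toxicity.
- Section 12 lets investigators leave out events expected in critical illness. Both randomized arms pass through that filter; a fixed outside benchmark may not have.

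At stake is whether the report can say how large an excess of harm the data support or exclude.

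**Working it through.** **Inputs.** From section 13.2: 50 subjects per arm ("a total of 100 subjects will be randomized 1:1 to receive cePolyTregs or placebo/SOC"), a 30% SAE rate, an illustrative 15/50, and the 45% benchmark. From section 8.8.6: anticipated mortality of 50%. From section 12.1: death is an SAE. Assumed here: a placebo count of 6/50, and a true SAE rate of 50% in both arms.

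**1. The plan's interval.** The exact (Clopper-Pearson) 95% interval for 15/50 is 0.1786 to 0.4461, which matches the stated 0.179 to 0.446. For 16/50 the upper limit is 0.467. The below-45% statement is therefore available at 15 or fewer events in an arm, and the other arm's count plays no part in it.

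**2. An excess that the one-arm statement does not show.** Take 15/50 on cells and 6/50 on placebo. The difference is 0.30 − 0.12 = 0.18. The Newcombe interval uses the Wilson limits of each arm: 0.1910 to 0.4375 for 15/50, and 0.0562 to 0.2380 for 6/50.

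- Lower limit: 0.18 − √[(0.30 − 0.1910)² + (0.2380 − 0.12)²] = 0.18 − 0.161 = 0.019
- Upper limit: 0.18 + √[(0.4375 − 0.30)² + (0.12 − 0.0562)²] = 0.18 + 0.152 = 0.332

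The same data fit a rate below 45% and give a difference of +18 points (95% CI +1.9 to +33.2), which excludes zero in the direction of harm.

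**3. No excess, but the one-arm statement fails.** Suppose the true SAE rate is 50% in both arms. Then P(X ≤ 15 | n = 50, p = 0.50) = 0.0033. The below-45% statement would be reached in 0.3% of trials although the cells do nothing. At the plan's 30% the same probability is 0.569.

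**4. Between-arm precision at the plan's own rate.** With 15/50 in each arm the Newcombe half-width is √[(0.30 − 0.1910)² + (0.4375 − 0.30)²] = 0.175, or ±17.5 points. The one-arm upper margin is 44.6 − 30 = 14.6 points. The between-arm figure is about 3 points wider, and it addresses product effect.

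**5. Would a formal test help?** For 15% against 30% with 50 per arm, power is about 43% at two-sided 5% (35% with Fisher's exact test). 80% power would need 121 per arm. An interval without a test is the proportionate choice.

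**6. The primary safety endpoint.** All the figures above concern SAEs, because that is the only adverse-event rate in section 13.2. The documents give no expected rate for related TEAEs of grade 3 or higher, so its precision can be neither reproduced nor computed from them.

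**The case against.** Descriptive safety reporting without a test is ordinary in a Phase 2a trial with 50 per arm, and step 5 shows that a test would be weak. Section 13.1 rules out formal comparison only; description by intervention received is planned, and a reader could compute an interval from the tabulated counts. All-cause mortality is a secondary efficacy endpoint (section 8.6.3), so section 13.8 already has it compared between arms. An unblinded DSMB is described in section 8.2. A separate SAP is promised and is not among the documents.

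Most of this stands, and it argues against asking for a test. It does not argue against planning an estimate. If the interval is left to the reader, its method and endpoints are not fixed in advance. A formal comparison placed only in the SAP would contradict section 13.1.

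Two stronger readings are tempting and should not be drawn:

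- A reader might infer that a doubling of the SAE rate over placebo would pass as reassuring. That needs a placebo rate of about 15% or less, which the documents do not give. Doubling the plan's own 30% gives 30/50, with an exact interval of 0.452 to 0.736, wholly above 45%.
- A reader might take the 45% sentence as a decision rule on the primary safety endpoint. It illustrates precision for either arm, concerns SAEs, and appears in no analysis section.

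**Conclusion.** The point holds in a limited form. The plan rules out formal comparison of a Part 2 primary endpoint, offers no difference or interval in its place, and states safety precision only for a one-arm SAE rate against a fixed benchmark. That does not use the randomized control for the purpose section 8.3 gives it.

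The two examples show the one-arm figure misleading in each direction. Both rest on assumed rates. The 6/50 placebo count is hypothetical. The 50% SAE rate is suggested, but not stated, by the plan's anticipated 50% mortality together with death counting as an SAE. The ±17.5 points uses the plan's own 30% and 50 per arm.

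This is a worthwhile, inexpensive improvement to the analysis. It does not make the planned descriptive tables wrong, and it leaves the primary efficacy comparison untouched.

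**What to change.** 1. In section 13.1 and the synopsis, replace the clause ruling out formal comparisons with: *the cePolyTregs minus placebo difference in the proportion of subjects with (a) related grade ≥3 TEAEs and (b) any SAE will be estimated with a 95% Newcombe (or Miettinen-Nurminen) confidence interval; no hypothesis test or alpha is attached.*
2. In section 13.2 and the synopsis, replace the 45% sentence with the between-arm precision: about ±17.5 points at 30% per arm with 50 per arm.
3. Reconcile the synopsis Safety Analyses paragraph with sections 13.1 and 13.3.1, so that placebo recipients are included in the safety summaries. If the synopsis were followed literally, even side-by-side description would be lost.

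The cost is a few lines of text and a slightly larger safety table, with no new data, patients or alpha. The downside is that the stated safety precision looks less favourable than the present one-arm figure.

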13.2 Determination of Sample Size

In Part 2 of the study, a total of 100 subjects will be randomized 1:1 to receive cePolyTregs or placebo/SOC administered as a single IV dose. Randomization will be stratified by study site and baseline WHO severity scale for COVID-19 pulmonary syndrome. Beigel (2020) reported that the rate of achieving a clinical severity score of 4 or better was 26.6% (67 out of 252 patients) within 14 days in the placebo arm among those with a symptom score ≥ 6 . Assuming that the distribution of time to recovery follows an exponential distribution, a 26.6% recovery rate within 14 days is equivalent to a median time to recovery of 31.4 days and a 46.1% recovery rate within 28 days. We expect cePolyTregs will halve the median time to recovery to 16 days, which is

equivalent to recovery rates of 45.5% and 70.2% within 14 and 28 days, respectively, under the exponential assumption. A sample size of 100 subjects (50 per group) will have 80% power to detect a reduction of 15.4 days in median time to recovery (or, equivalently, an improvement in recovery rate from 46.1% to 70.2% within 28 days) using the log-rank test at a two-sided type I error rate of 10%, based on Monte-Carlo simulations with 10,000 replicates.

The planned sample size will also provide a reasonably accurate estimate of the true SAE rate. The remdesivir study ([Beigel 2020](#)) reported that 30% of patients in the placebo group encountered SAEs. If 15 (30%) out of the 50 subjects in a study arm of the present study are observed to have an SAE, it will be possible to conclude that the true SAE rate is lower than 45%, at a 5% error rate, because the 95% confidence interval (0.179, 0.446) will exclude 45%.

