7 INTRODUCTION

7.1 COVID-19 Background

The zoonotic SARS-CoV-2 coronavirus was first identified in Wuhan, China in late 2019 from a set of patients with severe pneumonia (now denoted Corona Virus Disease-2019 or COVID-19). As of late July 2020, the virus has caused a global pandemic with more than 15 million confirmed infections and 635,000 deaths worldwide, >145,000 in the US (Johns Hopkins Coronavirus Resource Center). Approximately 12% of all patients infected with SARS-CoV-2 go on to develop severe disease requiring intensive care ([Phua 2020](#)), including a significant proportion who develop acute respiratory distress syndrome (ARDS). This disease is characterized by inflammation and diffuse alveolar damage, and respiratory failure, and can progress to shock and death ([Bradley 2020](#), [Xu 2020](#), [Wolfel 2020](#)). This end-stage disease is characterized by elevated inflammatory markers, shock and cardiac failure ([Siddiqi 2020](#)).

Mortality from COVID-19 is largely due to ARDS. ARDS pathogenesis is characterized by diffuse pulmonary inflammation, altered alveolar permeability, pulmonary edema, and hypoxemic respiratory failure ([Thompson, 2017](#)). Although ARDS can be triggered by a variety of predisposing conditions, including pneumonia, aspiration, sepsis, trauma, blood transfusion and pancreatitis, the most common cause of ARDS is infection. ARDS is defined clinically by acute onset hypoxemia (< 1 week and $\text{PaO}_2/\text{FiO}_2 < 300$ with a minimum of 5 cm H₂O PEEP) and radiographic evidence of pulmonary edema not fully explained by cardiac failure or fluid overload ([Force 2012](#)). Hypoxemia can range from mild ($\text{PaO}_2/\text{FiO}_2 < 300$) to severe ($\text{PaO}_2/\text{FiO}_2 < 100$), and the duration of respiratory failure can be variable. The annual incidence of ARDS is approximately 200 per 100,000 individuals and mortality remains approximately 40% ([Eworuke 2018](#)). Despite this burden of disease, little progress has been made in the development of novel therapies for ARDS since it was first described ([Ashbaugh 1967](#)).

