8.8.6 Study Discontinuation

The study may be stopped at the discretion of the Sponsor based on recommendations of the DSMB. The study may also be stopped pending DSMB evaluation of all available safety and PD data if any of the following occur:

- Any study drug-related death
- The occurrence of 3 deaths within 28 days post treatment in the first 5 subjects treated or, subsequent to the first 5 subjects, the observed mortality rate across the cumulative population of treated subjects exceeds the anticipated mortality rate of 50%
- Two CTCAE Grade 4 or 5 TEAEs that are deemed related to study drug
- An increase in the incidence of infections of special interest (pneumonia or infections involving pathogens not anticipated in a COVID-19 setting) beyond the expected background incidence

If the DSMB recommendation is to interrupt study dosing for all subjects or to pause enrollment, study dosing can be resumed, based on the recommendation of the DSMB, only after further review of all available safety data and applicable notifications of submission to appropriate regulatory agencies and institutional review committees, in line with country-specific regulations.

All deaths occurring during the study will be reviewed promptly by the DSMB as they occur. If at any point following enrollment of the first 5 subjects, the observed mortality rate across the cumulative population of treated subjects exceeds the anticipated mortality rate of 50%, the study will be halted.

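### The stated 80% power comes from a recovery model with no death term, although the protocol anticipates 50% mortality; with deaths counted as non-recoveries and no mortality benefit, power is lower, about 64-74% over the range examined.

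*Combined protocol and SAP*

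**What the plan says.** Section 13.2, repeated in the synopsis under Sample Size, states: "A sample size of 100 subjects (50 per group) will have 80% power" for a 15.4-day shortening of the median time to recovery. The test is specified as "using the log-rank test at a two-sided type I error rate of 10%, based on Monte-Carlo simulations with 10,000 replicates". The control input is 67 of 252 placebo patients (26.6%) recovered within 14 days in the cited remdesivir trial. Under an exponential assumption this becomes a median of 31.4 days and 46.1% recovered by Day 28. The active arm is given a median of 16 days, hence 45.5% by Day 14 and 70.2% by Day 28. The section does not mention deaths, a competing event or dropout.

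Three other places bear on this:

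- Section 13.1 on deaths in the primary analysis: "Data for subjects who fail to recover or die will be censored at Day 29". A subject who dies therefore stays in the risk set, unrecovered, to the end of the window.
- Section 8.8.6 and the synopsis stopping rules, where the study is to be halted if "the observed mortality rate across the cumulative population of treated subjects exceeds the anticipated mortality rate of 50" per cent. This cumulative rule names no arm and no time horizon.
- Section 7.1, on ARDS in general: "mortality remains approximately 40" per cent, also without a horizon.

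**The concern.** Eligible subjects are on mechanical ventilation, and the protocol itself expects many of them to die. Under the Day 29 rule a subject who dies before recovering can never supply a recovery event. A simulation without deaths gives every unrecovered subject the chance to recover up to Day 28, so it produces too many events and too wide a gap between the arms.

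The stake is how the result is read. If true power is nearer two-thirds than four-fifths, a null result is weaker evidence against an effect than the protocol tells its readers.

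**Working it through.** **1. Reproducing the plan's figure, with no deaths.**

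- Control recovery hazard: -ln(1 - 67/252)/14 = 0.02208 per day. Median ln2/0.02208 = 31.4 days. Day 28: 1 - exp(-28 × 0.02208) = 46.1%.
- Active recovery hazard: ln2/16 = 0.04332 per day. Day 14: 45.5%. Day 28: 70.3%, against 70.2% printed. Hazard ratio 0.04332/0.02208 = 1.962.
- Expected recoveries: 50 × (0.461 + 0.703) = 58.2.
- Schoenfeld: √(58.2/4) × ln(1.962) - 1.645 = 0.926, power 82.3%. Freedman: √58.2 × 0.962/2.962 - 1.645 = 0.833, power 79.8%. Log-rank simulation: about 82%.

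The stated 80% therefore reproduces, with no death term.

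**2. Where deaths drop out.** The Day 28 control rate equals 1 - (1 - 0.266)² = 46.1%. The recovery rate of Days 0-14 is applied again to everyone unrecovered at Day 14, including anyone already dead.

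**3. Fit with 50% mortality.** Active arm: 100% - 70.2% = 29.8% is the most that can die without recovering. To reach 50%, 50% - 29.8% = 20.2% of the arm must recover first and die later. Control arm: 46.1% + 50% = 96.1%, which is possible.

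**4. Power with deaths under the Day 29 rule.** Let r and d be constant recovery and death hazards. The proportion recovered by day t is F(t) = r/(r+d) × [1 - exp(-(r+d)t)]. The proportion dead before recovery has d in place of r in the numerator. For control, r and d were solved so that F(14) = 26.6% and death by Day 28 equals the chosen value. The active arm has recovery hazard 1.962r and the same d. Subjects who die are held unrecovered to Day 29, and the log-rank test is two-sided at 10% with 50 per arm.

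| Control deaths by Day 28 | r, d (control) | Recovered by Day 28, control vs active | Active deaths before recovery | Simulated power |
|---|---|---|---|---|
| none | 0.0221, 0 | 46% vs 70% | 0% | 82% |
| 28% (assumed) | 0.0251, 0.0170 | 41% vs 63% | 22% | 73-74% |
| 40% | 0.0273, 0.0281 | 39% vs 59% | 31% | 69% |
| 50% | 0.0300, 0.0412 | 36% vs 55% | 39% | 64-65% |

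At 50%, expected recoveries fall from 58.2 to 50 × (0.364 + 0.553) = 45.8.

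**5. Sensitivity to the way deaths are added.**

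- Stated hazards kept, plus a death hazard of ln2/28 in both arms (50% by Day 28 if nobody recovered): about 66%, with deaths before recovery of 39% and 31%.
- Stated hazards kept, death hazard set to give observed control mortality of 10%, 20%, 30%, 40% or 50%: 79%, 75%, 71%, 66% and 60%.
- Control calibrated as in step 4 at 50%, active arm calibrated to 45.5% at Day 14: 68%.
- Observed mortality of 50% in both arms: 39%.
- Step 4 at 50%, with the product also cutting the death hazard by 30%: about 82%. Active recovery by Day 28 is then 0.0589/0.0878 × [1 - exp(-0.0878 × 28)] = 61%, still below 70.2%.

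**The case against.** The best defence is that the recovery rates are already net of death. The control input is a crude 67/252, so deaths by Day 14 may already count as non-recoveries. If 46.1% and 70.2% are cumulative proportions on the same footing, power stays at 80-82%. This stands as a possible reading, and for that reason the documents do not support saying that the plan assumes nobody dies. But the doubling in step 2 then requires the recovery hazard among survivors to rise as deaths accumulate, which a constant-hazard model does not provide. It also caps active-arm deaths before recovery at 29.8%. Section 13.2 states neither condition.

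Three stronger conclusions might be inferred, and none is supported:

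- **That the figures are impossible, since 70.2% + 50% exceeds 100%.** The 50% belongs to a halting rule across cumulative treated subjects, with no arm and no horizon. Follow-up runs to Day 84, and recovery is the first qualifying day, so some subjects can recover and later die.
- **That true power is 65%.** That value needs constant hazards, a 28-day horizon, 50% mortality in the control arm and no effect on death. In that model active-arm mortality is about 39%, not 50%.
- **That the SAE precision statement fails in the same way.** Section 13.2 says that, with 15 SAEs in 50, "it will be possible to conclude that the true SAE rate is lower than 45" per cent. This is a conditional illustration, and its interval is not in dispute. Section 12 also keeps some events expected in critical illness out of AE reporting unless related or unexpectedly severe or frequent, so mortality need not equal the SAE rate. Replacing the example with 25/50 would equate SAEs with deaths.

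**Conclusion.** The point holds for the power statement. The arithmetic behind 80% is correct for a model without deaths, but Section 13.2 does not reconcile that model with the protocol's anticipated mortality or its Day 29 rule. If the exponential recovery model is kept and deaths are added with an equal death hazard in both arms, every scenario run falls below 80%. The calibrated models give about 73-74% at 28% control mortality, 69% at 40%, and 64-66% at 50% once the first alternative in step 5 is included. At 50%, power returns to about 82% if the death hazard is also cut by about 30%, a benefit that the plan does not state.

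These figures rest on constant, independent hazards, a recovery hazard ratio of 1.96 and a 28-day horizon. The 28% is an assumption found nowhere in the documents. The 40% is borrowed from the general ARDS figure in Section 7.1. The result is best reported as a range.

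**What to change.** In Section 13.2 and the synopsis:

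1. State the assumed 28-day mortality in each arm, and whether the 26.6%, 46.1% and 70.2% are net of deaths.
2. Rerun the simulation with death as a competing outcome and subjects who die held unrecovered to Day 29, as Section 13.1 specifies.
3. Replace the single 80% and the 46.1%/70.2% pair with recovery rates and power over a range of mortality, or state the mortality reduction that 80% power requires.
4. Reconcile the mortality assumption with the 50% in Section 8.8.6 and the synopsis stopping rules, giving the arm and horizon to which that figure refers.

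Leave the SAE illustration as it is. The cost is a rerun simulation and revised wording in two places. The number randomized, the endpoint and the primary test do not change. The stated power will probably be less favourable.
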